- Access to a support contact within the program for concerns or guidance. - Signposting to appropriate professional support services as appropriate (e.g., school-based counsellors, external mental health resources) if additional intervention is required.

Participation in the CDI-2 measures at T0 to T5

The PI will inform parents or main caretakers by phone if the girls score above 12 on the CDI-2 (the cutoff score for possible depression). They will be advised to contact their family doctor or the independent Health Care Professional for further guidance.

Participation in the RCADS-measures at T0 to T5

The PI will inform parents or caretakers by phone if the girls have a T-score greater than 65 on the RCADS (the cutoff score for possible anxiety disorder). They will be advised to contact their family doctor or the independent Health Care Professional for further guidance.

Participation in the intervention condition

1. *Participating in the online training sessions*

In this study, following psychotherapy literature, the potential for harm is defined as sustained deterioration in a girl's functioning that is *attributable to the prevention program* (Duggan et al., 2014). Evidence-based mindfulness programs are commonly described as educational or skills training programs, rather than forms of psychotherapy, but are often used to reduce psychological symptoms and stress in (sub)clinical populations. The literature on harmful effects of mindfulness programs is sparse. To be able to manage (potential) harm caused by the online training sessions skillfully and in a protocolled manner, we developed a risk management protocol to provide a consistent approach to the identification, reporting and follow-up of risks related to participation in the intervention condition. Before the first training session starts, the trainers explain that the girls are not allowed to talk about suicide, self-injury, sexual or physical abuse or eating disorders because of safety reasons. When girls talk about suicide, self-injury, sexual or physical abuse or eating disorders during the online training sessions, the trainer will stop the session. In these cases, the coordinating researcher will immediately (by no contact within 24 hours) contact the PI. The PI will contact the independent health care professional in case of severe problems. Depending on the situation, parents/main caretakers of both participants of the dyad or the school-mentor will be informed by the PI, depending on the specific topic. The PI will inform parents/main caretakers in situations of non-family related acute problems and will advise them to contact the family doctor or the independent health care professional. In case of severe family-related problems, the PI will call inform the school-mentor. We will inform the mentor in case of family-related acute problems, so that the school will be able to decide to use the Veilig Thuis Protocol. In severe cases the independent health care professional will also be consulted by the PI. In all situations, we protect the privacy of all participants. This implies that we only should inform parents/main caretakers or the mentor more in-depth when the participant initiated the conversation about suicide, self-injury, sexual or physical abuse, substance abuse or eating disorders. The training sessions will be continued after this procedure. All reported difficulties and support provided will be logged in the research team logbook. This part of the intervention protocol will be discussed and agreed with the headteachers/teacher-mentors of the participating dyads and will be explained in the participant information sheets for parents and girls. Moreover, following

study procedures of Baer and colleagues (2021; MYRIAD Mindfulness study), several questions will follow each training session and relating to unpleasant experiences during the sessions, perceived harm from the sessions, and support for any difficult experiences. Some used Likert scales whereas others requested free-text responses. A written introduction to these questions noted that the practice of mindfulness can increase awareness of the full range of human experiences, including difficult thoughts, emotions, and sensations. Girls then will be asked how often they had such experiences during the course (with response options ranging from “never” to “daily or almost daily”) and how upsetting these experiences will be (response options ranging from “not at all” to “extremely”). An open text response question will ask the girls to describe their unpleasant experiences during the mindfulness training in more detail. Next, harm will be defined for girls as being “worse off, in any way, after the course, than you would have been if you hadn’t done the course”. Girls will be asked how harmful the course is for them (response options ranging from “not at all” to “extremely”) and a free-response question will ask them to describe the harm in more detail. Finally, they will be asked if they had sought support for any difficult experiences and, if so, from whom and how helpful the support was. After each training sessions, trainers will send the questionnaires to the PI and she will contact girls who reported difficulties during the sessions within max. three days after the session, and she will provide appropriate support, eventually after consulting the independent Health Care Professional.

It is also possible that there will be possible deteriorations in girls’ functioning resulting from *frictions with the dyad friend* during the intervention period. The training program consists of fourteen online meetings in which the dyads participate together. Each dyad has its own trainer who provides all meetings. Every meeting the trainers discuss with the dyads how the cooperation with the app and the homework assignments went in the previous practice period. These discussions have a signaling function: trainers will invite the girls to share all their experiences. We assume that girls will share any problems regarding, for example, their motivation and any frictions or disagreements with the trainers (or that these are observable by the trainers based on verbal and non-verbal behavior during the meetings), so that solutions can be found together. If necessary, trainers may also seek general advice from the teacher-mentors. These possible problems, solutions and results are shared by the trainers during the interventions, so that trainers can offer uniform advice as much as possible.

The use of the app is monitored at the individual level twice a week by the researchers. When girls write about suicide, self-injury, sexual or physical abuse or eating disorders in their Diary, the coordinating researcher will immediately (by no contact within 24 hours) contact the PI. The PI will contact the independent health care professional in case of severe problems.

Depending on the situation, the parents/main caretakers of the participant or the school-mentor will be informed by the PI, depending on the specific topic. The PI will inform parents/main caretakers in situations of non-family related acute problems and will advise them to contact the family doctor or the independent health care professional. In case of severe family-related problems, the PI will call inform the school-mentor. We will inform the mentor in case of family-related acute problems, so that the school will be able to decide to use the Veilig Thuis Protocol. In severe cases the independent health care professional will also be consulted by the PI. In all situations, we protect the privacy of all participants. This implies that we only should inform parents/main caretakers or the mentor more in-depth when the participant disclosed about suicide, self-injury, sexual or physical abuse, substance abuse or eating disorders. All reported difficulties and support provided will be logged in the research team logbook. This part of the intervention protocol will be discussed and agreed with the headteachers/teacher-mentors of the participating dyads and will be explained in the participant information sheets for parents and girls

When girls do not fill in the Diary and Moodtracker for more than three days in a row, the researchers will pass this on to the trainers, because this may indicate motivation problems, and whether this is caused by mutual friction. But girls may also be sick, for example, which causes them to lose track of the app for a while. During the next meeting, the trainers will discuss the causes of non-response with the dyads and jointly look for solutions. This information, possible solutions and results will also be shared by the trainers during the intervisions.

2. Using the app

Because the App yourself Happy app will collect high-risk personal (health) data in order to monitor the program fidelity and to supervise the trainers (this process will be the responsibility of the PI), the Chief Privacy Officer of the Rotterdam University of Applied Sciences ([name]) and a Data Steward ([name]) conducted a Data Protection Impact Assessment, which was finalized in December 2022 with an approved addendum for the current study in January 2023. Rotterdam University of Applied Sciences and YipYip (the company who is leading on the technical development and design of the App yourself Happy app) have conducted a 'Data Verwerkersovereenkomst'. In sum: all risks have been analyzed and this process resulted in several mitigating measures. The only identified residual risk with moderate risk status concerns the following: 'Appropriate agreements have been made with YipYip and Rotterdam University of Applied Sciences about the processing of personal data recorded in a processing agreement. YipYip has an ISO/IEC27001:2017 and NEN 7510-1:2017 certification. YipYip uses the 'subverwerker' Google Cloud Platform. The company is

located in the United States, but data storage takes place in the Netherlands. YipYip has indicated to have appropriate agreements with Google and is Google ISO 27001 and Netherlands Norm 7510 certified. Any residual risk at American cloud providers cannot be ruled out.

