8.1.2 Secondary study parameters/endpoints

T0, T1, T2, T3, T4, and 1-year follow-up measures T5 (girls)

Self-reported depressive symptoms/disorder

The self-reported level of depressive symptoms will be assessed using the Child Depression Inventory 2 (CDI-2; Boddien, Braet, & Stikkelbroek, 2016), a 28-item questionnaire. Each item provides three response options, scored from 0 to 2 (e.g., 0 = “I am sad once in a while,” 1 = “I am sad many times,” and 2 = “I am sad all the time”), with respondents selecting the option that best describes their experience. Higher scores indicate greater depressive symptoms, with total scores ranging from 0 to 56. A score of 12 or higher is considered clinically relevant. The CDI-2 demonstrates strong internal consistency, test–retest reliability, and convergent validity

(Bodden, Braet, & Stikkelbroek, 2016). For the current study the item concerning suicide has been left out, resulting in a 27-item questionnaire.

Self-reported generalized anxiety symptoms/disorder

Self-reported generalized anxiety disorder will be assessed using the Dutch version of the Generalized Anxiety Disorder (GAD) subscale from the Revised Children's Anxiety and Depression Scale (RCADS) (Chorpita et al., 2000). This subscale consists of six items (e.g., "I worry about things") and evaluates generalized anxiety on a 4-point scale (0 = never, 3 = always). The RCADS is known for its strong psychometric properties, demonstrating excellent reliability and validity (Chorpita et al., 2000; Chorpita, Moffitt & Gray, 2005). The official Dutch translation of the RCADS, which is available for free, will be used. Previous studies have shown that the Dutch version of the Generalized Anxiety Disorder (GAD) subscale has good internal consistency, validity, and sensitivity to change (Kösters et al., 2015).

Self-reported positive and negative affect

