All analyses will be conducted in structural equation modeling program Mplus (v 8.7 or higher; Muthén and Muthén, 1998-2017). Model fit will be determined using the comparative fit index (CFI, critical value $\geq .95$), the root mean square error of approximation (RMSEA, critical value $\leq .06$) and the standardized root mean square residual (SRMR, critical value $< .08$; Hu & Bentler, 1999). When appropriate, standard errors will be adjusted for clustering of dyads within schools using a sandwich estimator (Williams, 2000). For hypotheses that include mediation analysis (hypothesis 1 & 5) we will use 10.000 bootstrap resamples with replacement and bias-corrected 95% confidence intervals to test these indirect effects (Preacher and Hayes, 2004). When appropriate, differences in (indirect) pathways between the intervention and the control arm will be estimated using the DIFFtest option in Mplus (when using the WLSMV estimator) or the Satorra Bentler chi-square difference test (Satorra & Bentler, 2001; when using the MLR estimator).

Handling of protocol non-adherence and missing data

The way the questionnaires are administered online makes it impossible to skip a question. Participants who do not complete a questionnaire will receive one or more reminders. Missing data during the follow-up period (e.g., due to unavailability during a certain measurement wave or due to dropout) will be handled using Full Information Maximum Likelihood (FIML) estimation.

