11.3 Objection by minors or incapacitated subjects

The study targets female adolescents aged 10-12 years. Parents or main caretakers must provide written consent, but only if their child is willing to participate. Twelve-year-olds must also sign an IC form, in addition to obtaining consent from their parents or main caretakers. Signed IC from both parents or main caretakers is essential for participation. Participants are free to withdraw from the study at any time, without any further consequences. Special attention will be given to addressing any resistance or objections during the assessments

with minors. In cases of resistance, study participation will be terminated. Examples of resistance include (1) the adolescent or her best friend becoming upset, (2) the adolescent or her best friend arguing, or (3) the adolescent or her best friend requesting to stop the video recording or to end their participation in the study. Researchers will adhere to the Code of Conduct for resistance in minors (CCMO, 2017).

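### The CDI-2 parent-alert rule (section 9.2.2) starts one point above the clinical cut-off in section 8.1.2, so a girl scoring exactly 12 triggers no call

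*Protocol*

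**What the plan says.** Section 8.1.2 describes the CDI-2 as a 28-item scale with a total from 0 to 56. On scoring it says "Each item provides three response options, scored from 0 to 2", and on interpretation "A score of 12 or higher is considered clinically relevant". It then adds that for this trial the "item concerning suicide has been left out, resulting in a 27-item questionnaire". Neither the range nor the cut-off is restated for the shortened form.

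Section 9.2.2, under "Participation in the CDI-2 measures at T0 to T5", has the principal investigator phone the parents or main caretakers "if the girls score above 12 on the CDI-2 (the cutoff score for possible depression") and advise them to contact the family doctor or the independent health care professional. The rule is not limited to one arm.

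Section 10.2, on missing data, says: "The way the questionnaires are administered online makes it impossible to skip a question".

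On the minor point, the block of section 9.2.2 on deterioration is introduced as grounds for discontinuing participation, and item 1 lists those grounds. The heading of item 2 covers reconsidering either participation or withdrawal. Under a single lead-in it lists distress that is improving or significant, distress for which the programme is expected to help, and a girl's clear wish to withdraw.

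**The concern.** The two sections name the same number and treat it differently. In section 8.1.2 a total of 12 is inside the clinically relevant range; in section 9.2.2 it is outside the alert range, although the same sentence calls 12 the cut-off. Staff who apply the written rule, or code it as a strict inequality, will not phone the parents of a girl at 12.

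Other safeguards exist, but none is tied to a CDI-2 total of 12. In both arms there is the anxiety alert at a "T-score greater than 65 on the RCADS (the cutoff score for possible anxiety disorder"), the rule in section 11.3 that "In cases of resistance, study participation will be terminated", and free withdrawal. The intervention arm also has trainer check-ins, harm questions after each session, app monitoring and escalation of self-harm content. The control arm has none of these intervention-arm measures, and from T1 its questionnaires arrive by email (section 8.3). With the suicide item removed, the CDI-2 total is the only depression score that triggers a call.

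The minor point is one of direction. Item 2 does not say which of its conditions leads to continuing and which to stopping.

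**Working it through.** **Inputs.** Clinically relevant: total of 12 or more (8.1.2). Alert: total above 12 (9.2.2). Item scores: 0, 1 or 2 (8.1.2). No item can be skipped (10.2). Full form 28 items, administered form 27 items (8.1.2).

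**Step 1, ranges.** Full form: 28 × 2 = 56, which reproduces the stated maximum. Administered form: 27 × 2 = 54, which the protocol does not state.

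**Step 2, the two thresholds compared.** Completed totals are whole numbers, so above 12 means 13 or more.

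| Set of totals | Rule as written (above 12) | 12 or higher |
|---|---|---|
| Clinically relevant, no alert | 12 only | none |
| Alert, not clinically relevant | none | none |

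The result is the same for the range 0 to 54 and for 0 to 56.

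**Step 3, the omitted item.** Assume that the cut-off of 12 belongs to the 28-item form, beside which it is stated. Let X be the 28-item total and s the score the omitted item would have had (0, 1 or 2). The administered total is X − s, so it lies 0 to 2 points lower. The combinations with X ≥ 12 that produce no alert are:

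- Above 12 (missed if X − s ≤ 12): (X, s) = (12,0), (12,1), (12,2), (13,1), (13,2), (14,2). That is six.
- 12 or higher (missed if X − s ≤ 11): (12,1), (12,2), (13,2). That is three.
- Recovered by the change: (12,0), (13,1), (14,2). That is 6 − 3 = 3, exactly those with an administered total of 12.

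These are counts of score combinations, not of girls. The protocol gives no distribution with which to weight them.

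**Step 4, item 2 of section 9.2.2.** Sorted by direction, improving distress and an expected benefit point to continuing or resuming; significant distress and a wish to withdraw point to stopping. All stand under one lead-in. A lost negation (not improving, not beneficial) would make the whole list point to stopping, but that is an inference. A two-way list is also possible, because section 8.4 has the principal investigator ask whether lessons could continue later in the school year.

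**The case against.** The strongest reply is that this is loose wording. The sentence in section 9.2.2 itself calls 12 the cut-off, and the anxiety rule beside it has the same form ("T-score greater than 65 on the RCADS (the cutoff score for possible anxiety disorder"), so a score above the cut-off may be no more than a drafting habit. Nothing shows that the sponsor chose 13. That is plausible, but it does not rescue the rule. If 12 was meant, the correction costs nothing. If 13 was meant, the protocol acts only above its own definition of clinical relevance and gives no reason.

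A second reply is that the consequence is small: one score point and one missing advisory call. Rescoring helps too. In cohort 1 the waves from T0 to T4 are about two months apart (section 3), so a girl at 12 who rises by one point is caught at the next wave. Section 9.2.2 also offers a support contact and signposting to professional help, and lists sustained worsening of depression as a sign of deterioration. All of this limits the harm and stands. It does not help a girl who stays at 12, and T5 comes a year after T4.

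A third reply is that 12 or higher on 27 items may not be the right threshold either, since three of the six missed combinations remain. This is correct. The protocol gives no cut-off for the 27-item form, so none can be derived from it. The correction makes the document consistent; it does not settle that question.

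On item 2, the heading is openly two-directional, the lead-in is permissive, item 1 already holds the grounds for stopping, and withdrawal is free at any time. That is why the point is minor.

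**Conclusion.** The concern holds. Followed as written, the alert rule misses exactly one total, 12, which the protocol itself classes as clinically relevant. This rests only on whole-number totals, which follow from the item scoring and the ban on skipped questions. The rule covers up to 320 girls at six waves, but that is the number screened, not the number missed; the latter cannot be computed.

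The further shift of 0 to 2 points from the omitted item rests on the assumption that the cut-off belongs to the 28-item form. The unsorted list in item 2 is a minor ambiguity.

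Neither point affects the primary analysis or the sample size. The threshold should be fixed because it governs a safety action for children and the remedy is nearly free.

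**What to change.** In section 9.2.2, set the alert at 12 or higher on the administered 27-item total (range 0 to 54), and use the same words and range in section 8.1.2. Whether to allow for the omitted item as well, for instance with a lower threshold, is a separate decision for the sponsor and should be stated either way.

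Split item 2 of section 9.2.2 into two labelled lists. Conditions for withdrawal: distress significant or not improving, programme not expected to help, girl wishes to stop. If intended, conditions for continuing or resuming: distress improving, programme expected to help. The sponsor should confirm the intended meaning first.

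The cost is one reworded threshold, one short list split, a note to trainers and study staff, and additional phone calls only for girls who score exactly 12.

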9.2.3 Suspected unexpected serious adverse reactions (SUSARs)

Not applicable.

9.3 Annual safety report

Not applicable.

9.4 Follow-up of adverse events

Not applicable.

9.5 Data Safety Monitoring Board (DSMB) / Safety Committee

Not applicable.

10. STATISTICAL ANALYSIS

10.1 Primary study parameter(s)

To test the primary hypothesis, the following statistical analyses will be conducted:

Hypothesis 1 “Girls in the intervention group will have a greater reduction in co-rumination (primary outcome) about distress and difficult emotions and feelings, (and thereby) internalizing symptoms (depression/anxiety, secondary outcomes) and negative affect (secondary outcome) during the intervention period, immediately after the intervention period and after one-year follow-up, relative to girls in the control condition” will be tested via a multi-level (within level = girls within dyads; between level = dyads) parallel process, dual latent growth curve model (with co-rumination measured via self-report).

For analysis with co-rumination measured via self-report (T0 to one-year follow up T5), we will use multi-level parallel process, dual latent growth curve (LGM) models, with intervention arm as the exogenous predictor variable, growth rate of co-rumination (primary outcome) as the mediating variable and growth rate of internalizing symptoms as (correlated) secondary outcome variables. The mediator and primary and secondary outcome variables will be

modelled on both the individual (within) level and on the dyadic (between) level. This way, the between-level intervention effects will be adjusted for variation between individuals in co-rumination (primary outcome) and internalizing symptoms (depression/anxiety, secondary outcomes) at the within-level. Note that we have no a priori hypotheses regarding the nature of the growth patterns of the mediator and outcome variables and that they may be best captured by either a linear or a non-linear slope. We will adjust the analyses accordingly. For a (simplified) visual representation of this model, please see Figure 2. For a more technical description of this model, see Preacher, Zyphur, & Zhang, 2010; Preacher, Zhang, & Zyphur, 2011).

[figure not shown]

Figure 2. Simplified visual representation of a multilevel, duals process latent growth model with a predictor (e.g., intervention condition), mediator (e.g., co-rumination, primary outcome) and secondary outcomes (e.g., anxiety/depression). Ovals represent latent variables; squares represent observed variables. Double headed arrows represent (residual error) correlations, single headed arrows represent regression paths. Paths of interest are in bold.

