4.4 Sample size calculation

Multi-level models are used with individuals nested in dyads. To determine the required sample size for this cRCT study power analyses were conducted using Optimal Design Plus – Evidence (Raudenbusch, 2011). These analyses were based on an alpha level (α) of .05, with three measurement points (baseline and two follow-up measurements), and an intraclass correlation (ICC) of .40 between two friends (ρ). This ICC was derived from observed ICCs for perceived support within friendship dyads ($n = 266$ pairs) in an existing dataset of adolescents with an average age of 13. For average risk girls (M), the multilevel power analysis was based on an expected effect size (Cohen's d) of 0.50, indicating a small to medium effect. The power analysis showed that, to achieve a power level of 0.80, at least 122 average-risk friendship dyads would need to be included. However, we will aim to oversample to a maximum of 160 dyads in order to be able to compensate for loss to follow up .

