feelings. The items are designed to assess a more intense form of discussing problems, going beyond typical self-disclosure. For this study, 9 items (one for each content area) will be used to evaluate co-rumination as screening and at T0, T1, T2, T3, T4, and the 1-year follow-up at T5. This shorter version is referred to as the Co-rumination Questionnaire-Short (CRQ-Short). These items include: “We talk about problems that my friend or I are having almost every time we see each other”, “When we see each other, if one of us has a problem, we will talk about the problem even if we had planned to do something else together,” “When my friend has a problem, I always try really hard to keep my friend talking about it.,” “When I have a problem, my friend always tries to get me to tell every detail about what happened,” “When we talk about a problem that one of us has, we’ll talk about every part of the problem over and over,” “When we talk about a problem that one of us has, we talk about all of the reasons why the problem might have happened,” “When we talk about a problem that one of us has, we try to figure out every one of the bad things that might happen because of the problem,” “When we talk about a problem that one of us has, we spend a lot of time trying to figure out parts of the problem that we can’t *understand*,” and “When we talk about a problem that one of us has, we talk a lot about how bad the person with the problem feels.” Rose (2002) found that her 27-item co-rumination measure was unifactorial, and a factor analysis of the 9-item version used by Hankin et al. (2010) similarly identified a single factor. In the studied sample, the 9-item measure demonstrated strong internal consistency, with Cronbach’s alpha values of 0.89 at Time 1, 0.91 at Time 2, and 0.91 at Time 3. Girls will respond to the items using a 5-point Likert scale ranging from 0 (“not at all true”) to 4 (“really true”), with the overall score calculated as the mean of the nine items. Rose et al. (2007) reported excellent internal consistency, good test–retest reliability, and strong validity for the measure.

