8.2 Randomisation, blinding and treatment allocation

Dyads will be randomly assigned in a 1:1 ratio to either the intervention group (max 80 dyads; $n = \text{max } 160$ girls) or the control group (TAU; max 80 dyads; $n = \text{max } 160$ girls) by an independent researcher using CASTOR EDC, a web-based randomization program compliant with Good Clinical Practice (GCP) guidelines. Ideally, randomization will occur on a single day after completing the screening phase. If this is not feasible (e.g., due to time constraints), randomisation will proceed in batches of 50 dyads (100 girls) and on classroom level. The median of the screening scores will be calculated, and dyads where one or both girls above the median will be included. These dyads will then be randomly assigned to the intervention or control group using a block randomisation procedure (50% allocated to each group). Allocation will be concealed through a computer-generated list in a secure web-based application. However, due to the organisational structure of the prevention program, participants, parents, schools, and researchers will be aware of group assignments. As the trial follows an open-label design, unblinding will not occur.

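### The primary growth model names arm as its only predictor and leaves out the screening CRQ-Short, the one co-rumination score clearly taken before randomisation

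*Protocol*

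**What the plan says.** Section 10.1 sets out the primary analysis as a two-level growth model (girls within dyads), "with intervention arm as the exogenous predictor variable, growth rate of co-rumination (primary outcome) as the mediating variable". The waves are fixed: "For analysis with co-rumination measured via self-report (T0 to one-year follow up T5"), so T0 enters as the first repeated outcome and screening does not enter. The growth form is open, since "they may be best captured by either a linear or a non-linear slope". The only adjustment described separates variation between girls within a dyad from variation between dyads.

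Section 8.1.1 has the same instrument at every occasion: "9 items (one for each content area) will be used to evaluate co-rumination as screening and at T0, T1, T2, T3, T4", and again at T5. Sections 4.2 and 8.2 use the screening score for the median cut, and section 8.4 uses it when a girl continues with a new friend. No analysis uses it.

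On timing, section 8.2 says "Ideally, randomization will occur on a single day after completing the screening phase". It does not place T0 before or after allocation. Section 3 puts T0 in September 2025 for cohort 1 and the programme from October 2025, so T0 precedes the lessons, but that does not settle its order relative to randomisation.

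**The concern.** The trial already collects a pre-randomisation score on the primary outcome scale, and the stated model does not use it. Arm is allocated by dyad and so varies only between dyads. Separating within-dyad variation therefore does not adjust the arm contrast for baseline co-rumination.

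Precision is at stake. If arm is free to predict the T0 intercept, the test on the growth rate is a comparison of change from T0 and carries the noise of the T0 score. If the arms are held equal at T0, most of that noise is removed and screening adds a little more. The sample is capped at 160 dyads and section 4.4 states no dropout rate, so precision from data already in hand has value. Screening also precedes any dropout, so including it makes the missing-at-random assumption behind FIML somewhat easier to defend; that benefit is not quantified here.

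**Working it through.** **The plan's own figure.** No figure in the protocol concerns baseline adjustment. Section 4.4 gives 122 dyads for power 0.80 at d = 0.50, with a within-dyad ICC of .40. With alpha .05 taken as two-sided, those inputs give 2 × (1.960 + 0.842)² / 0.50² = 62.8 girls per arm. The design effect is 1 + (2 − 1) × 0.40 = 1.40, and 62.8 × 1.40 / 2 = 44 dyads per arm, or 88 in all. The 122 cannot be rebuilt because its repeated-measures inputs are not given. That does not show it is wrong, and it is a separate matter, but it offers no firm base for a power statement here.

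**Inputs for the precision check**
- From the protocol: 1:1 allocation by dyad; cohort 1 waves at months 0, 2, 4, 6, 8 and 20 (section 3); ICC .40 (section 4.4).
- Assumed: screening one month before T0; a girl's own correlation falling in a straight line from r₁ at lag 1 month to r₂ at lag 20 months and flat after that; friend cross-correlation 0.40 times her own. Three (r₁, r₂) pairs are used: (.6, .4), (.7, .5) and (.5, .3). The protocol gives no such correlations. With the cross-correlation in this form, the ICC cancels from the ratios below.

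**Worked case: T4 with (.6, .4)**
1. Lag 8 (T0 to T4): .6 − .2 × 7/19 = .526. Lag 9 (screening to T4): .6 − .2 × 8/19 = .516. Screening to T0: .6.
2. Arm free at T0, so change from T0: variance proportional to 2(1 − .526) = .947.
3. Arms equal at T0: 1 − .526² = .723. Ratio .723/.947 = .763.
4. Arms equal at T0 plus screening: R² = (.526² + .516² − 2 × .526 × .516 × .6)/(1 − .6²) = .340. Residual .660; ratio .660/.947 = .697.
5. Screening alone, if the arms are already equal at T0: .697/.763 = .914, a cut of about 9%.

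**All cases.** Variance of the arm effect by generalised least squares, relative to arm free at T0 without screening. Columns 2 to 4 are for (.6, .4), (.7, .5) and (.5, .3).

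| Specification and target | .6/.4 | .7/.5 | .5/.3 |
|---|---|---|---|
| Arms equal at T0, T4 | .763 | .813 | .713 |
| Arms equal at T0, T5 | .700 | .750 | .650 |
| Arms equal at T0, slope | .771 | .809 | .726 |
| Equal + screening, T4 | .697 | .731 | .665 |
| Equal + screening, T5 | .667 | .706 | .629 |
| Equal + screening, slope | .739 | .773 | .700 |
| Arm free at T0 + screening, T4 | .993 | .991 | .994 |
| Arm free at T0 + screening, T5 | .967 | .960 | .971 |
| Arm free at T0 + screening, slope | .962 | .955 | .967 |

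Letting the correlation keep falling beyond 20 months moves the slope ratio with equality and screening to at most .778.

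**Reading the table**
- Screening added where the arms are already equal at T0: cuts of 3-10% (for example .731/.813 = .90 at T4, .629/.650 = .97 at T5).
- Screening added where arm stays free at T0: cuts of about 1-5%.
- Equality and screening together, against arm free at T0: 27-34% at T4, 29-37% at T5, 22-30% for the slope.

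**A different covariance.** With a random intercept and slope (intercept share of variance 0.4 to 0.8, assumed slope SDs), the T0-T5 slope ratio is 0.77-0.99 for equality at T0, 0.73-0.96 with screening added, and 0.945-1.00 for screening with arm free at T0. The smallest gain for equality plus screening is thus 1 − .963, about 4%, and screening with a free intercept can gain almost nothing.

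**The case against.** The strongest case against is that nothing in section 10.1 is wrong or biased, that covariate lists and path constraints are often left to an SAP, and that the larger gains depend on a path the text does not mention. Section 10.1 names only the growth rate as what arm acts on, and Figure 2 is not available. If arm has no path to the intercept, the arms are already equal at T0 and only the small gain from screening remains.

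Much of this stands. It limits the size and makes the point one of efficiency. It does not remove the point, because section 10.1 goes beyond a bare outline: it names predictor, mediator, outcomes, waves, levels and an adjustment, and the adjustment it names does not help the arm contrast.

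A reader might infer more than the protocol supports:
- That T0 is discarded. It is the first modelled wave and informs both intercept and slope.
- That T0 is a pre-randomisation score. The protocol does not say so. Under section 8.4, a girl whose dyad stops after the first lesson may start again with a new friend, and the new dyad then takes a fresh T0. That T0 follows allocation in an open-label trial.
- That every analysed girl has a screening score. Section 8.4 describes consent and T0 for the new friend, but no screening.
- That power would rise from 0.80 to some higher figure. The 0.80 belongs to 122 dyads, which the stated inputs do not reproduce, and the aim is up to 160.

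Selection on the screening score may also lower its correlation with later scores, which would shrink the gain.

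**Conclusion.** The point holds as a modest, nearly free gain in precision. The stated model omits the only co-rumination score that the protocol clearly places before randomisation, and it leaves the treatment of T0 undetermined.

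Under the assumed correlations, screening alone is worth about 1-10% of the variance of the arm effect. The larger figures, 22-30% for the slope and 27-37% at T4 or T5, need two conditions that the protocol does not settle: T0 taken before allocation, and arm otherwise free on the intercept. Even then, a different covariance can bring the slope gain down to about 4%. The primary test is on the growth rate, so the slope figures are the relevant ones if growth is linear. A reader might take the omission as a source of bias; under randomisation it is not. The change is advisable but not essential to the trial's validity.

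**What to change.** - Regress the co-rumination intercept and slope on the screening CRQ-Short, entering the girl's deviation from her dyad mean at the within level and the dyad mean at the between level.
- State in sections 8.2 and 8.3 whether T0 is taken before or after randomisation, and in section 10.1 whether arm predicts the intercept.
- Only if T0 precedes allocation, also hold the arms equal at the T0 intercept. Do not apply that constraint to re-paired dyads whose T0 follows allocation.
- Give a rule for the analysis of re-paired dyads, including a new friend with no screening score.
- Report the unadjusted model as a sensitivity analysis.

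The cost is a few lines of model specification and a sentence on timing. No new data are needed, but the change should be fixed before outcome data are examined by arm.
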